Bacterial vaginosis Vaginal pH is 5.0 or higher. Treat regardless of the presence of symptoms.	
 
1st choice: Metronidazole 400 or 500 mg orally twice per day for 7 days OR Metronidazole 2g single oral dose.
 
2nd choice: Tinidazole 2g orally once a day for 2 days or 1g per day for 5 days.
 
Alternative: Clindamycin 300 mg orally twice per day for 7 days
 
	
 
Metronidazole 2g single oral dose is a less effective treatment for BV than the 7-day treatment. Only give a single oral dose if you are worried that the patient will not be adherent for 7 days.
 
Women should be encouraged to wear clean underwear daily, not wash inside the vagina (and if this cannot be avoided, to use clean plain water only), and use hormonal contraception to prevent recurrence.
 
Male partners are not treated but women should be told that BV-associated bacteria can be passed between sexual partners. Their male partners should be encouraged to improve their penile hygiene and clean underneath the foreskin regularly.
 

Vaginal candidiasis When symptoms typical for vaginal candidiasis are present: White, curd-like, odorless vaginal discharge with vaginal itching and/or burning.	
 
1st choice: Fluconazole 150 mg single oral dose
 
2nd choice: Clotrimazole 200 mg pessaries every night for 3 nights
 
	
 
Do not treat without lab confirmation; do not treat if asymptomatic)
 
Male partners are not notified but if a male partner has symptoms of balanoprosthitis, he can be given 1% Clotrimazole cream to be applied for 14 days.
 
Patients should be counseled to abstain from sex or use condoms, until symptoms have cleared.
 

Diagnosis	Treatment Other Follow-Up		

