
 
Syndrome: Genital warts/condylomata
 
RU Physician to inspect and palpate external genitalia/inguinal area and conduct speculum exam to differentiate between the various genital ulcer/bubo syndromes and genital warts.
 
	
 
In the case of mild warts, provide treatment with 20% podophyllin solution.
 
In the case of severe warts/condylomata, refer for cryotherapy.
 
	
 
In female sex workers, also consider the possibility of anal genital warts
 
Treatment of male partners is not indicated. Women should be adviced to abstain from sex or use condoms during outbreaks to avoid HPV transmission to sexual partner(s).
 

 
Urinary tract infection
 
Do urinalysis test only when UTI symptoms are present.
 
Treat when urinalysis test shows at least 1+ leukocytes or nitrites. Also consider treatment if there is blood in urine that cannot be explained by menstrual blood or spotting related to contraceptive use.
 
	
 
1st choice: Ciprofloxacin 500 mg orally twice per day x 7 day. Alternative: Ceftriaxone IM 125 twice per day x 5 days.
 
	- No follow-up and no male partner treatment required.
Cervical cytology (not done at RU)	- Refer all high-risk women for cervical cancer screening if they have not undergone screening in the past five years.	- No male partner referral required.

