#### **CONTRAINDICATIONS:**

- Doxycyclin, tetracyclin, ciprofloxacin and cotrimoxazole should not be used during pregnancy and lactation; doxycyclin may reduce the effectiveness of hormonal contraception. Azithromycin and ceftriaxone may be used by pregnant women.
- Metronidazole and fluconazole can be used only once during the first trimester of pregnancy; patients must not drink alcohol while taking metronidazole.
- Benzathine benzyl penicillin is contraindicated in case of allergy or when using hormonal contraception.
- Doxycyclin and erythromycin should be taken with meals.

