7.3 Overall costs

The overall salary costs of the RU personnel, the costs of clinic supplies, laboratory supplies, and the overhead costs will be synthesized to estimate costs of the procedures as performed during the WISH study.

	Rwandan	Euros
	Francs	
Exchange rate used (per xx/xx/xxxx)		
Salary per month of physician		
Salary per month of nurse		
Salary per month of laboratory staff		
Salary per month of receptionist		
Medication		
Ciprofloxacin 500 mg, single oral dose		
Ciprofloxacin 1000 mg, single oral dose		
Ciprofloxacin 500 mg, twice per day, 3-day course		
Ciprofloxacin 500 mg, twice per day, 7-day course		
Doxycycline 100 mg, twice per day, 7 day-course		
Doxycycline 100 mg, twice per day, 14 day-course		
Doxycycline 100 mg, twice per day, 21 day-course		
Metronidazole 2 grams, single oral dose		
Metronidazole 500 mg, twice per day, 7 day-course		
Metronidazole 500 mg, twice per day, 14-day course		
Ceftriaxon 250 mg, single im dose		
Fluconazole 150 mg, single oral dose		
Clotrimazole 200 mg pessaries, 3 day-course		
Benzathine benzyl penicilline, 2.4m IU, single im dose		
Benzathine benzyl penicilline, 2.4m IU, three im doses		
Acyclovir 400 mg, thrice per day, 7 day-course		

Clinic and laboratory supplies	
Glove, price per unit	
Gloves, price used per participant (3 x 2 gloves)	
Vacutainer EDTA tubes 4.5 ml, per participant	
Vacutainer needles, per participant	
Urine container, per participant	
HIV Rapid Test Determine, per participant	
HIV Rapid Test Unigold, per participant	
HIV ELISA (at LNR), per participant	
Determine Syphilis Rapid Test, per participant	
Syphilis RPR (SpinReact), per participant	
NOVA pregnancy test, per participant	
NOVA urine dipstick, per participant	
GeneXpert machine (2 slots), including desktop	
GeneXpert CT/NG cartridge, per participant	
TV OSOM test, per participant	
Merete vaginal pH swabs, per participant	

The overall costs will be used for cost-effectiveness comparisons of syndromic management versus WISH procedures. These will be reported separately, in a tertiary SAP.

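### Protocol Appendix 14.3 does not fully fit its own contraindication list for pregnant or lactating women: UTI, BV/TV and LGV rows need reconciling, and the UTI ceftriaxone dose shows no unit

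*Protocol*

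**What the plan says.** Protocol 5.1 admits women known to be pregnant, and the exclusion criteria in 5.2 do not mention lactation. Pregnancy alone makes both WISH risk scores positive (SAP 4.1), so pregnant women are routinely tested for CT/NG and syphilis. All women with vaginal pH 5.0 or above are treated for BV. Protocol 6 refers the reader to Appendix 14.3 for treatment details.

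The contraindication list that closes Appendix 14.3 makes three relevant statements:

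- "Doxycyclin, tetracyclin, ciprofloxacin and cotrimoxazole should not be used during pregnancy and lactation"
- "Azithromycin and ceftriaxone may be used by pregnant women"
- "Metronidazole and fluconazole can be used only once during the first trimester of pregnancy"

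The rows above the list include:

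- UTI: first choice "Ciprofloxacin 500 mg orally twice per day x 7 day", then "Alternative: Ceftriaxone IM 125 twice per day x 5 days".
- BV: first choice "Metronidazole 400 or 500 mg orally twice per day for 7 days OR Metronidazole 2g single oral dose", with the follow-up instruction "Only give a single oral dose if you are worried that the patient will not be adherent for 7 days".
- TV: single-dose or 7-day metronidazole, the longer course being preferred if BV is also present unless poor adherence is suspected.
- Inguinal buboes without ulcers: the LGV component is doxycycline for 21 days, with no alternative.

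In the SAP, the only ceftriaxone item in the 7.3 price list is "Ceftriaxon 250 mg, single im dose". Section 5.6 counts treatments erroneously given or not given, with WISH procedures as the reference.

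**The concern.** A clinician treating a pregnant or breastfeeding participant has to apply the row and the list together. In several places that cannot be done from the text. For UTI, the list removes the first choice and leaves an injectable entry whose amount cannot be read. For LGV, it removes the only drug. For BV and TV, it imposes a limit that the rows neither repeat nor allow for.

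The group concerned is one for which the protocol makes special provision, so a table that cannot be applied to it as written bears on patient safety. There are two smaller consequences for the analysis. Where the reference is ambiguous, SAP 5.6 cannot say whether a treatment was a mistake. And some regimens listed as alternatives have no price in SAP 7.3.

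**Working it through.** No figure in the plan is to be reproduced, because the protocol made no formal sample size calculation and the issue is textual. The check sets each row against the list.

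**1. Rows against the drugs barred in pregnancy and lactation.** Here *not barred* means only that the drug is absent from the bar, not that it is suitable.

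| Row | Barred by the list | Listed and not barred |
|---|---|---|
| UTI | ciprofloxacin | ceftriaxone 125, no unit |
| LGV | doxycycline | none |
| CT | doxycycline | erythromycin |
| NG | ciprofloxacin | ceftriaxone, unit given |
| Chancroid | ciprofloxacin | ceftriaxone, unit given |
| PID | ciprofloxacin, doxycycline | ceftriaxone with erythromycin |
| Syphilis | doxycycline (an alternative) | benzathine penicillin, erythromycin |
| BV | none | metronidazole (limited in first trimester), tinidazole, clindamycin |
| TV | none | metronidazole (limited in first trimester), tinidazole |

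Two rows fail on the bar itself. LGV is left with nothing, and UTI with an entry that cannot be read as written. The list's permission for ceftriaxone covers pregnancy only, so its position in lactation is not addressed.

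**2. The first-trimester limit on metronidazole.** The list does not define what a single use is.

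- Read as one dose: the 7-day regimen is 2 x 7 = 14 administrations against a limit of 1. Only the single-dose option would meet the limit, but the BV row withholds it unless non-adherence is feared, and the TV row prefers 7 days when BV is present. The passages then contradict each other.
- Read as one course: one 7-day course counts once, and there is no contradiction. The limit applies only to repeat treatment.

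SAP 4.1 gives a further reason for the single dose in its treatment footnote (alcohol use). Pregnancy is not given as a reason in either document.

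**3. Azithromycin.** It has one mention in the contraindication list and none in any regimen row, in the named drugs of the SAP 4.1 treatment table, or in the SAP 7.3 price list.

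**4. Size, for UTI.** Protocol 4.3 expects 115 UTI cases per 500 women, and SAP 2 reports 705 enrolled.

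- 115 / 500 x 705 = 162 cases.
- The pregnant or lactating share is in neither document. Assumed at 5% to 20%: 0.05 x 162 = 8 and 0.20 x 162 = 32.

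The 162 is best taken as a ceiling. Protocol 4.3 assumes no opt-outs, and Appendix 14.3 calls for testing only when symptoms are present and bases treatment mainly on a qualifying dipstick. No comparable figure can be formed for LGV.

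**5. SAP lists.** Section 7.3 prices no erythromycin, no azithromycin and no UTI ceftriaxone course. It also omits tinidazole and clindamycin. Current pregnancy (SAP 4.1) and breastfeeding (SAP 3) are recorded; gestational age is not among the tabulated items.

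**The case against.** The strongest reply is that Appendix 14.3 is a summary. Its treatment column says to follow the latest Rwandan guidelines, Protocol 6 and 6.2 defer to those guidelines and to the site's SOP, and SAP 7.1 says that SOP was updated for WISH. A general table followed by a list that limits it is also an ordinary layout. This stands in part: it lowers the practical risk, and harm in practice is not shown. It does not supply the missing unit, define the metronidazole limit, or give the LGV row an option that is not barred.

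The unit may also have been lost in text extraction, since the nearby PID cell repeats a line many times and is visibly corrupted. That is a fair caution. The source PDF should be checked before this limb is pressed.

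A reader might infer more than the documents support:

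- *That the whole table fails in pregnancy.* CT, NG, chancroid, PID and syphilis each keep a listed drug outside the bar, and BV has clindamycin. The PID row also refers women with a missed period to hospital.
- *That several first-trimester rules conflict.* There is one rule, undefined, and it contradicts the rows on only one of its two readings.
- *That the absence of azithromycin leaves CT untreatable.* Erythromycin is listed, and the azithromycin statement is permissive.
- *That the UTI entry must be wrong because it is far from the other ceftriaxone entries.* If the 125 is milligrams, 125 x 2 x 5 = 1,250 mg in ten injections, against 250 mg in one. But those entries are for other indications, and ciprofloxacin regimens in the same table also vary by indication. The comparison is not evidence of error.
- *That the price list neglects pregnancy specifically.* Its gaps are wider than that. SAP 4.1 leaves most antibiotic categories open, so any regimen given can still be counted, and cost-effectiveness is deferred to a separate SAP.

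**Conclusion.** The point holds for four rows. The UTI alternative has no unit in the text as read. The BV and TV rows do not carry a first-trimester limit that is itself undefined. The LGV row lists only a barred drug. The unmatched mention of azithromycin is a lesser discrepancy.

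It matters for safety because eligible women are treated from this table, and for two descriptive outputs: the mistake counts and the treatment costs. The accuracy measures do not depend on treatment and are untouched. Scale is uncertain: the 8 to 32 women for UTI rest on an assumed share and a case count that is probably too high. The BV/TV contradiction rests on reading the limit as one dose, and the UTI limb rests on the PDF also lacking a unit.

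**What to change.** - **Protocol Appendix 14.3.** The sponsor should reconcile the UTI, BV, TV and LGV rows with the contraindication list, against the national guideline the table says it follows. This means stating the unit of the UTI ceftriaxone entry after checking the source PDF, saying whether the metronidazole limit is a dose or a course, and aligning the drugs named in the list with those in the rows. Which dose or rule is right is for the sponsor to establish.
- **SAP 7.3.** Add a price for every regimen actually dispensed that the list omits, such as erythromycin, azithromycin or a UTI ceftriaxone course, if used.
- **SAP 5.6.** Count mistakes against the protocol and SOP in force at the time. Flag as not classifiable the cases in pregnant or breastfeeding women where the table was ambiguous. Do not re-judge past care against a later table: data collection ended in March 2017, and the SAP tables hold no gestational age with which to apply a first-trimester rule.

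The cost is a correction to a short appendix and a few SAP rows. No new data or visits are needed, because pregnancy and breastfeeding are already recorded.

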#### **CONTRAINDICATIONS:**

- Doxycyclin, tetracyclin, ciprofloxacin and cotrimoxazole should not be used during pregnancy and lactation; doxycyclin may reduce the effectiveness of hormonal contraception. Azithromycin and ceftriaxone may be used by pregnant women.
- Metronidazole and fluconazole can be used only once during the first trimester of pregnancy; patients must not drink alcohol while taking metronidazole.
- Benzathine benzyl penicillin is contraindicated in case of allergy or when using hormonal contraception.
- Doxycyclin and erythromycin should be taken with meals.

1.1 WISH objectives and endpoints

The current standard of care for urogenital infections in Rwanda is syndromic management. Many urogenital infections are asymptomatic and therefore completely missed, and the management of vaginal discharge syndrome (VDS) is known to be suboptimal. We conducted the WISH (Women's Improvement of Sexual and reproductive Health) study to address this problem. Data collection took place at the Rinda Ubuzima (RU) research clinic in Kigali, Rwanda, from July 2016 to March 2017. The study was sponsored by the University of Liverpool (UoL).

The primary objective of the WISH study is to evaluate whether it is feasible to improve urogenital infection care in high risk women in Kigali, Rwanda (see 'study population' below), using point of care (POC) diagnostic testing for HIV, Trichomonas vaginalis (TV), and bacterial vaginosis (BV) in all women; POC testing for Neisseria gonorrhoeae (NG), Chlamydia trachomatis (CT), and syphilis in pregnant women and women assessed to be at high risk for these infections using a risk scoring questionnaire; and management of vaginal candidiasis, urinary tract infection (UTI), genital ulcers/inguinal buboes, and lower abdominal pain (LAP) in women reporting relevant symptoms. The secondary objectives of the study are 1) to evaluate the performance and 2) cost effectiveness of the POC tests for CT/NG, TV and BV; and 3) to obtain the opinions of stakeholders (clinicians, programme implementers and policymakers) about the potential improvement of urogenital infection care in Rwanda as well as 3b) the potential roll-out of novel vaginal microbicides and multipurpose prevention technologies for HIV and pregnancy prevention as soon as efficacious products become available. This statistical analysis plan (SAP) describes the statistical analyses to be undertaken to achieve the primary objective and the first secondary objective (POCT performance), as well as some related exploratory analyses. The other secondary objectives will be analysed separately.

Primary objectives	Primary endpoints
 Implement improved urogenital infection care services and monitor and evaluate these services 	 Monitoring and evaluation indicators, such as: Inputs: Procurement experiences/costs, infrastructure and training requirements; Activities/outputs: Numbers of clients counselled and risk scored, diagnostic tests conducted, infections diagnosed and treated, and referrals made; staff time required for each activity; time spent at the clinic for each client trajectory; Outcomes/impacts: Improvements of access to and quality of services (from client satisfaction survey, staff interviews).
Secondary objectives	Secondary endpoints
 Compare performance of syndromic management, POCT, and gold standard molecular testing for the diagnosis of NG, CT, TV, BV, and candidiasis. 	 Sensitivity, specificity, PPV, and NPV for: TV, BV: Syndromic vs POCT of everyone vs gold standard Candidiasis: Syndromic vs gold standard NG, CT: Syndromic vs POCT after risk scoring vs POCT (= gold standard) of everyone. The POCT test is a molecular test and is considered to be a gold standard in this SAP.

1.2 WISH study population

We enrolled adult women (18 years or older) living in the city of Kigali who were at high risk of HIV/urogenital infections (defined as having had more than one sexual partner OR having been treated for a sexually transmitted infection (STI) in the 12 months prior to enrollment) regardless of

the presence of current urogenital symptoms. Each woman could participate in the WISH study only once. Women were excluded when they were participating in another health intervention study or were unfit for participation as judged by the PI, but they were not excluded when they were known HIV-positive and/or pregnant. Unmarried women aged 18-20 required written informed consent of a parent or guardian (as per Rwandan law) in addition to their own consent; however, this was no longer needed after 7 November 2016 because the age of majority was lowered from 21 to 18 in the Rwandan law.

1.3 WISH study procedures

All participants attended a Main Visit, during which the following procedures were done in the order given: eligibility check, informed consent procedures, assignment of Patient Identification Number (PID), face-to-face interview including CT/NG and syphilis risk scoring, counselling (the participant could choose the topics she wanted to be counselled on herself), and a pelvic and bimanual examination if the participant reported relevant and moderate/severe urogenital symptoms (see paragraph 4.1, section "Pelvic, bimanual and physical examinations performed at Main and Additional Visits", for details).

Participants were offered the following additional services:

- a) Voluntary counselling and testing (VCT) for HIV.
- b) Urine pregnancy test if indicated.
- c) POC testing for UTI if UTI symptoms were present.
- d) POC testing for TV and BV regardless of symptoms, and management of vaginal candidiasis based on symptom-reporting and/or signs during a pelvic examination (if applicable).
- e) POC testing for syphilis and/or CT/NG if considered at risk by risk scoring (such as being pregnant).
- f) Syndromic management of LAP, genital ulcer syndrome (GUD) and inguinal buboes.
- g) Treatment and partner notification and treatment as appropriate, and referrals to antenatal, family planning, HIV and cervical cancer screening care.

Services were available for free at RU's research clinic for the duration of the project. Services were generally delivered within one half day. However, women could choose to leave before all results were available, and be contacted by study staff when results were available, which was particularly relevant for women undergoing CT/NG POC testing (this was performed on the Cepheid GeneXpert platform, which takes about 90 minutes).

Additional Visits took place when participants opted not to wait for test results, for partner notification and treatment, if urogenital symptoms did not resolve after treatment, and for other reasons that are summarised in this SAP. Women could notify partners themselves or allow RU staff to contact partners. They could also opt out of partner notification of specific partners, for example, if there was a risk of domestic violence. Participants who developed new urogenital symptoms were referred to local clinics because each woman was allowed to participate in the WISH study only once.

1.4 STI syndromic management: WHO and Rwandan guidelines

The WHO published its STI syndromic management guidelines¹ in 2003 to allow for diagnosis and treatment of STIs in resource-poor settings where laboratory testing is not available and physical examination skills are scarce. The original idea was that each symptom syndrome (vaginal discharge syndrome (VDS), lower abdominal pain (LAP), genital ulcer disease (GUD), etc) would be treated for

¹ World Health Organization, 2003: Guidelines for the Management of Sexually Transmitted Infections.

all organisms that might cause the syndrome. This was later expanded by the addition of physical examinations (if available), and the possibility to tailor the guidelines to local STI epidemics as well as person-centered risk assessments. A next version of the guidelines was published in 2008² but the VDS and LAP algorithms for women were unaltered. Flowcharts of the WHO algorithms relevant for the WISH study are shown in appendix 8.1.

The Rwandan STI management guidelines were published in 2010³ with an update in 2013⁴ (see appendix 8.2). Only the treatment guidelines, but not the diagnostic algorithms, were revised in this update. The Rwandan STI management guidelines differ substantially from the WHO guidelines:

- Both guidelines contain two different VDS algorithms: one with and one without a speculum and bimanual examination (and the WHO guidelines also incorporate the possibility of local wet mount or Gram stain microscopy). However, the Rwandan guidelines assume that the clinician can distinguish between mucopurulent cervical discharge and/or cervicitis (which is to be treated for CT/NG/TV) and non-mucopurulent vaginal discharge (which is to be treated for BV/TV/candidiasis). We believe that speculum examinations will rarely be available, and when available, will mostly be used to identify PID, GUD, buboes, condylomata, and other visible/palpable pathologies, but cannot be reliably used to distinguish between different types of discharge. In this SAP, we will therefore only use the VDS algorithms in the absence of a speculum and bimanual examination when evaluating algorithm performances.
- The Rwandan VDS algorithms incorporate a predetermined set of questions for CT/NG risk scoring, as well as CT/NG treatment when a woman's partner has urethritis complaints. The WHO guidelines do provide the possibility for risk scoring but state that risk scoring should be guided by local epidemiology. *In this SAP, when evaluating the performance of the Rwandan guidelines, we will follow the Rwandan risk scoring as outlined in the algorithm.* One of the possible risk factors in the Rwandan guidelines is "2 or more sexual partners" but no time frame is given; we will use 2 or more sexual partners in the past 12 months. When evaluating the performance of the WHO guidelines, we will assume high risk for CT/NG based on the local epidemics in our research communities.
- In the Rwandan VDS algorithms, candidiasis is diagnosed based on the presence of unusual vaginal discharge and a low CT/NG risk score, while in the WHO guidelines candidiasis is only treated in the presence of typical signs and symptoms (vulval oedema/curd-like discharge, vulval erythema or excoriations). *In this SAP, we will follow each respective guideline when evaluating the performance of that guideline.*
- In the Rwandan algorithms, all female sex workers (FSWs) without symptoms are to receive presumptive treatment for NG, CT and TV. However, when they do report symptoms, the usual syndromic algorithms are to be used and no presumptive treatment should be given. No definition of FSW is given. In this SAP, we will define sex work by self-reported exchange of sex for money and/or goods in the past 12 months, and we will follow the Rwandan guidelines.

Flow diagrams of the WISH algorithms, as described in section 1.3, are shown in appendix 8.3.

2. Participant disposition

The number of participants was dictated by the available budget and no formal statistical power calculations were performed. 705 participants were enrolled in the study.

² World Health Organization, 2008: Report of the Expert Consultation and Review of the Latest Evidence to Update Guidelines for the Management of Sexually Transmitted Infections.

³ Republic of Rwanda – Ministry of Health, 2010: National Guide on the Care of Sexually Transmitted Infections – Manual of the Care Provider.

⁴ Republic of Rwanda – Ministry of Health, 2013: National Guidelines for Prevention and Management of HIV, STIS & Other Blood Borne Infections.

Women heard about the study during recruitment activities (recruitment meetings organised by RU staff, leaflets) or word of mouth. From 4 July 2016 to 2 September 2016, RU staff conducted all recruitment activities with the help of three Community Mobilisers (two were former female sex workers; one was a community organizer), as had been done previously in many RU studies. They referred high risk women to recruitment sessions in the community (conducted by RU staff) and handed out leaflets. However, this method attracted too many women who tested positive on the risk scores (mostly because many of them were sex workers). From 5 September 2016 until the week of 13 March 2017, RU staff no longer worked with the Community Mobilisers, but instead, performed the following recruitment activities: providing information and recruitment leaflets at non-governmental women's organizations (such as women's cooperatives), monthly umuganda community meetings, district hospitals, local health centers, pharmacies, and at a local family planning clinic. Earlier participants from the WISH study (especially testing negative on risk scores) were also encouraged to refer friends and family. These new strategies did indeed attract fewer women who tested positive on the risk scores. The numbers of women who were approached (at a meeting, by leaflet, or by word-of-mouth); subsequently did or did not attend the RU clinic for a Main Visit; and did or did not proceed to the informed consent procedures are not known. Data were only collected from women who attended the RU clinic after they had given informed consent.

Participants were allowed to voluntarily withdraw from the study for any reason at any time. The PI was also allowed to discontinue participants (for example, if this was deemed in the best interest of the participant). The reason(s) for withdrawal or discontinuation were recorded in the participant's records.

Participant disposition	N = 705	
N women enrolled	705	
N women excluded by PI at the Main Visit	0	
N women who completed their Main Visit	705	
N women who did not complete their Main Visit	0	
N women who withdrew their informed consent after Enrolment	0	
Participant disposition	n (%) N = 705	
N Additional Visits attended		
N women who attended one Additional Visit		
N women who attended multiple Additional Visits		
Reasons for Additional Visits ¹ :		
 To withdraw informed consent 		
 To obtain results and/or treatment: left Main Visit prior to receiving all results 		
- For speculum/bimanual exam because this could not be completed at Main Visit		
 For additional sampling/testing because this could not be completed at Main Visit 		
- For speculum/bimanual exam and/or additional testing because symptoms did not resolve		
(ongoing untreated infection, re-infection, or treatment failure)		
 To have a new urogenital symptom investigated or to repeat screening for HIV/STIs or urogenital infections² 		
– For couple counselling, potentially in conjunction with HIV testing of a male partner		
– To report an (S)AE and/or social harm		
 To ask questions or express concerns 		
 Other, specify [additional categories to be made if necessary] 		
N women aged 18-20 who required consent of a parent or guardian ³		
N women aged 18-20 who did not require consent of a parent or guardian ³		

Abbreviations: AE = adverse event; PI = Principal Investigator; STI = sexually transmitted infection.

- 1. May total to more than 100% because one woman could attend Additional Visits for multiple reasons.
- 2. These women should subsequently be referred to a local clinic.
- 3. The age of majority in Rwanda changed from 21 to 18 years of age during the study. The % is of all women aged 18-20.

3. Description of the study population

All women participating in the WISH study underwent a face-to-face interview with a clinician during the Main Visit. Questions were asked about sociodemographics, sexual history, reproductive and contraceptive history, and general medical history. All of the data below are self-reported by the participant.

Demographic data	n (%) N = 705
Kigali sector where participant lives:	11 705
- Gikondo	
- Kimihurura	
- Remera	
- Muhima	
- Other: [categories to be made]	
Age in years: median [IOR]	
Marital status:	
- Never married	
- Married	
- Divorced	
- Widowed	
Highest educational level attained:	
- No schooling	
- Primary school not completed	
- Primary school completed	
- Secondary school not completed	
- Secondary school completed	
- More than secondary school	
Sexual history	n (%)
N male sex partners in lifetime: median [IQR]	
N male sex partners in past 12 months: median [IQR]	
N sex partners in past month: median [IQR]	
New sex partner in the past three months	
Currently has a main sex partner	
Reported length of relationship with main sex partner: median [IQR]	N = xxx
Currently lives together with main partner: - Yes	N = xxx
Main partner is circumcised:	N = xxx
- Yes	
- No	
- Does not know	
Knows or suspects that main partner has had other sexual partners in past 12 months:	N = xxx
- Yes	
- No	
- Does not know	
N vaginal sex acts in the past two weeks: median [IQR]	

N anal sex acts in the past two weeks: median [IQR]		
Has had anal sex in the past two weeks		
Frequency of condom use during vaginal sex in the past two weeks:		
- Always		
- Sometimes but not always		
- Never		
Used a condom during last vaginal sex act		
Exchanged sex for money or goods in past month		
Exchanged sex for money or goods in past 12 months		
N male sex partners in lifetime if exchanged sex in past 12 months: median [IOR]	M = xxx	
N male sex partners in past 12 months if exchanged sex in past 12 months: median [IQR]	N = xxx	
Reproductive and contraceptive history	n (%)	
N pregnancies in lifetime: median [IQR]		
N deliveries in lifetime: median [IQR]		
N miscarriages/stillbirths in lifetime: median [IQR]		
N induced abortions in lifetime: median [IQR]		
N premature born children (i.e. < 37 weeks) in lifetime: median [IQR]		
N children born alive in lifetime: median [IQR]		
N children alive at visit date: median [IQR]		
Length between visit date and last birth in months: median [IQR]		
Currently breastfeeding		
Has a regular menstrual cycle:		
- Yes		
- No, irregular		
- Amenorrhea due to progestin-only contraception		
- Amenorrhea due to pregnancy or postpartum period		
- Amenorrhea due to menopause		
Has ever used a product to prevent pregnancy		
If yes, product(s) used in lifetime ¹ :		
- Combined estrogen/progestin pills [describe brands in footnote]		
- Progestin-only pills [describe brands in footnote]		
- Progestin injections [describe brands in footnote]		
- Progestin implant [describe brands in footnote]		
- Copper IUD		
- Participant is sterilised		
- Other [categories to be made as needed]		
Currently using a product to prevent pregnancy		
If yes, product currently using ¹ :		
- Combined estrogen/progestin pills [describe brands in footnote]		
- Progestin-only pills [describe brands in footnote]		
- Progestin injections [describe brands in footnote]		
- Progestin implant [describe brands in footnote]		
- Copper IUD		
- Participant is sterilised		
- Other [categories to be made as needed]		
General medical history	n (%)	
Has ever had surgery		
Has a chronic disease [describe in footnote]		

Has long-term medications [describe in footnote]		
Took antibiotic or antifungal treatment in the previous two weeks [describe in footnote]		
Is currently taking an antibiotic or antifungal [describe in footnote]		
Has ever had an allergic reaction to a medication or other commercial product		
Has been tested for HIV in the past		
If yes, number of times tested for HIV: median [IQR]	N = xxx	
Known to be HIV-positive prior to Main Visit		
Treated for an STI in the past		
If yes, number of times treated for an STI: median [IQR]		
Has been treated for BV in the past		
If yes, number of times treated for BV: median [IQR]		
Has been treated for a yeast infection/vaginal candidiasis in the past		
If yes, number of times treated for a yeast infection/vaginal candidiasis: median [IQR]	N = xxx	
Has been treated for a UTI in the past		
If yes, number of times treated for a UTI: median [IQR]		

Abbreviations: BV = bacterial vaginosis; IQR = interquartile range; IUD = intra-uterine device; NA = not applicable; STI = sexually transmitted infection; UTI = urinary tract infection.

1. May total to more than 100% because women could report multiple methods.

4. Primary objectives

